### **8.3. Variables**

For this observational study, the following variables will be recorded: demographic, medical history (including date and stage of disease at diagnosis and at progression), surgical treatment, histology, blood count and blood biochemistry, first-line treatments, associated adverse events, clinical efficacy and history of treatment with axitinib, including treatment line (second, third, etc.), dose, reason and date of start of treatment, disease risk criteria before onset, comorbidities, associated adverse events, concomitant medication and subsequent treatments, as well as the patient’s condition (alive, deceased) and the last date on which contact was made.

A complete description of the variables, including the operational definitions, will be detailed in the Statistical Analysis Plan of the study.

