**Analysis population****All analyses will be performed with evaluable patients.**

The CRF contains the information related to the eligibility criteria as binary variable (Yes/No) for each of the described items.

Several of these criteria can be verified with the data recorded in the CRF. This verification is performed in order to prevent the inclusion of non-evaluable participants in the statistical report and prior to the start of any analysis.

These patients will be considered screening failure, and in the statistical report they will thus be included in a table of patient disposition together with the patients screening failure initially confirmed by the sponsor.

The criteria to be verified in the patient CRFs to define the evaluable population are described below:

- An "evaluable" patient must have received at least one dose of axitinib prior to inclusion in the study: it must be verified that the "Starting dose" and the "Treatment start date with axitinib" have been specified in "Treatment with axitinib". This date must be prior to the date of signing the informed consent (for patients who are still alive at enrolment).

- Inclusion requirement *Patients must have received axitinib as second-line treatment or further line*: it must be verified that there is information concerning a first-line treatment in the "First-line treatment" section.

- IC1: *Evidence of a personally signed and dated informed consent document indicating that the patient (or his/her legal representative) has been informed of all relevant aspects of the study. Informed consent will only be obtained from patients who are still alive.*

It must be verified that the date of signing the informed consent is specified (for patients who are still alive at enrolment).

Noted that for patients already dead before the study inclusion, the CII could be "No".

- IC2: *Aged 18 or over.*

It must be verified that the age calculated with respect to the date of the baseline visit is  $\geq 18$  years.

- IC3: *Histologically confirmed diagnosis of advanced renal cell carcinoma, with at least one radiological evaluation of the disease according to RECIST 1.1 criteria.*

It must be verified that the following data have been indicated: Date of first diagnosis, Tumour stage at disease diagnosis, Date of advanced disease diagnosis, Stage of advanced disease, Metastasis location, Best treatment response (first-line treatment).

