          - Reason for starting this treatment (DP in the 1st line treatment/Toxicity in the 1st line treatment/Other, specify)
          - Start date
          - End date
          - Reason for treatment withdrawal (DP/Toxicity/Other, specify)
          - Has there been disease progression? (No/Yes, specify date)
          - Best treatment response (CR, PR, SD, DP/Not evaluable).
            - Date of the best response obtained
        - 3rd-line treatment
          - Drug
          - Starting dose
          - Reason for starting this treatment (DP in the 2nd line treatment/Toxicity in the 2nd line treatment/Other, specify)
          - Start date
          - End date
          - Reason for treatment withdrawal (DP/Toxicity/Other, specify)
          - Has there been disease progression? (No/Yes, specify date)

- 
- Best treatment response (CR, PR, SD, DP/Not evaluable).
    - Date of the best response obtained
  - Treatment with axitinib
    - Treatment line in which it was received.
    - Reason for starting treatment with axitinib (DP in previous treatment line/Toxicity in previous treatment line/Other, specify).
    - Risk criteria at the initiation of treatment with axitinib
      - Time from first diagnosis to systemic treatment less than 1 year (Yes/No/Unknown)
      - ECOG/PS (current status) (Yes/No/Unknown)
      - LDH >1.5 x ULN (Yes/No/Unknown)
      - Haemoglobin < LLN (Yes/No/Unknown)
      - Corrected calcium >10 mg/dl (Yes/No/Unknown)
      - Presence of 2 or more metastatic sites (Yes/No/Unknown)
      - Platelets > ULN (Yes/No/Unknown)
      - Neutrophils > ULN (Yes/No/Unknown) (value)
      - Lymphocytes (Yes/No/Unknown) (value)
      - Smoking habits (Smoker/Non-smoker/Former smoker)
    - Presence of comorbidities
      - Kidney failure (Yes/No)
        - If yes, specify, Creatinine Clearance (Mild, 60-89 ml/min/ Moderate, 30-59 ml/min/ Severe, 15-29 ml/min/ End Stage, <15 ml/min/ Dialysis)
      - Liver failure (Yes/No)
        - If yes, specify, Child Pugh (A/B/C)
      - Cardiovascular (Yes/No)
        - If yes, specify (multi-response question)
          - Decreased LVEF, specify %
          - Heart failure
          - Previous arrhythmia
          - Previous ischaemia
          - Controlled HTN, specify number of antihypertensive agents
          - Other, specify
      - Respiratory disease (Yes/No), specify
      - Other comorbidity (Yes/No), specify
    - Start date of treatment with axitinib

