## 7 DEFINITION OF VARIABLES AND OBJECTIVES

In addition, the following variables will be calculated from the CRF data:

NOTE: In patients with dates after the date of the IC visit / signature, the date of the IC visit / signature has been considered as the date of the last check. Due to the retrospective nature of the study, no data can be collected after the patient was included in the IC study / signature.

- Age (years) of patient at time of visit= (Visit date – Date of birth) / 365.25
- Age (years) at first diagnosis= (Date of first diagnosis – Date of birth) / 365.25
- Age (years) at the initiation of axitinib= (start date of axitinib – Date of birth) / 365.25
- Number of metastatic locations = sum (Lymph nodes, CNS, Hepatic, Pulmonary, Bone, Other).
- • Neutrophil / lymphocyte ratio. It will be categorized as follows:  $\leq 3$ ,  $> 3$ . "Before the beginning of the first line" and "At the beginning of treatment with axitinib" will be analyzed. This ratio is not calculated on axitinib suspension because there is no current lymphocyte value data in that part of the CRF.
- Time (months) between first diagnosis and nephrectomy = (Date of nephrectomy – Date of first diagnosis) / 30.4375. A list with the information (site, patient, date of first diagnosis, date of nephrectomy and the calculated time) in cases in which the time is negative (with date of nephrectomy before or equal to date of first diagnosis) will be displayed, and these cases will not be included in the descriptive analysis
- Time (months) between first diagnosis and radiotherapy = (Date of radiotherapy – Date of first diagnosis) / 30.4375. A list with the information (site, patient, date of first diagnosis, date of radiotherapy and the calculated time) in cases in which the time is negative (with date of radiotherapy before or equal to date of first diagnosis) will be displayed, and these cases will not be included in the descriptive analysis.
- Time (months) between first diagnosis and 1st-line treatment = (Date of the initiation of 1st-line treatment – Date of first diagnosis) / 30.4375. A list with the information (site, patient, date of first diagnosis, date of 1st-line treatment and the calculated time) in cases in which the time is negative (with date of 1st-line treatment before or equal to date of first diagnosis) will be displayed, and these cases will not be included in the descriptive analysis

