 $(\text{Dose increase date or Dose reduction date} - \text{Start date of treatment with axitinib}) / 30.4375$
  - Duration (months) of subsequent treatments =  
 $(\text{Date of end of subsequent treatment or of latest follow-up if not suspended} - \text{Date of start of subsequent treatment}) / 30.4375$ . In the case of several subsequent treatments per patient, proceed as follows: the duration in months of each of the subsequent treatments will be calculated (from the start date to the end date or last check if it continues). This will be done for all subsequent treatments and then proceed to make the sum per patient of all durations of subsequent treatments

- Progression-Free Survival (PFS, in months) =  
 (Date of Disease Progression on treatment with axitinib or death from any cause – Date of start of treatment with axitinib) / 30.4375  
 If there is no progression or death, the case is censored as  
 PFS (months) = (Date of latest follow-up – Date of start of treatment with axitinib) / 30.4375
- Time to progression (TTP, in months) =  
 (Date of Disease Progression – Date of start of treatment with axitinib) / 30.4375  
 If there is no progression, the case is censored as  
 TTP (months) = (Date of latest follow-up – Date of start of treatment with axitinib) / 30.4375
- Overall Survival (OS, in months) = (Date of death – Date of start of treatment with axitinib) / 30.4375  
 If death has not occurred, the case is censored as  
 Overall Survival (OS, in months) = (Date of latest follow-up – Date of start of treatment with axitinib) / 30.4375
- Overall Survival since the start of first-line treatment (OS, in months) = (Date of death – Date of start of first-line treatment) / 30.4375  
 If death has not occurred, the case is censored as  
 Overall Survival (OS, in months) = (Date of latest follow-up – Start date of first treatment) / 30.4375
- Patient subgroups
  - A-Long-term responders: comprising patients with PFS  $\geq 9$  months.
  - B-Refractory (primary): comprising patients with best response to treatment = PD. This date is collected in the CRF form “axitinib treatment”.
- MSKCC risk group (described in appendix 11.1.). It will be analysed “Before the beginning of the first line”. These calculations will be performed on patients who have data on all the variables involved (in the case of a patient who does not have data on all the variables but has > 2 factors, it will be classified in the “Poor” risk group.

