Risk groups are defined considering the following five factors (Favourable, Intermediate, Poor):

- ECOG/PS <1 (related to KPS <80)
- Time from first Diagnosis to Systemic Treatment less than 1 year
- LDH >1.5 x ULN
- Corrected calcium >10 mg/dl
- Haemoglobin < LLN

---

The risk groups are as follows:

- Favourable: 0 factors
  - Intermediate: 1 or 2 factors
  - Poor: >2 factors
- 
- Heng (or IMDC) risk group (described in appendix 11.1.). It will be analysed “at the beginning of the axitinib treatment” and “on the axitinib discontinuation”. These calculations will be performed on patients who have data on all the variables involved (in the case of a patient who does not have data on all the variables but has > 2 factors, it will be classified in the “Poor” risk group.

Risk groups are defined taking into account the following six factors (Low, Intermediate, High):

- ECOG/PS <1 (related to KPS <80)
- Time from first Diagnosis to Systemic Treatment less than 1 year
- Corrected calcium >10 mg/dl
- Haemoglobin < LLN
- Neutrophils > ULN
- Platelets > ULN

The risk groups are as follows:

- Favourable: 0 factors
  - Intermediate: 1 or 2 factors
  - Poor: >2 factors
- 
- Risk group according to MSKCC Criteria for patients previously treated with a TKI (defined in appendix 11.1). It will be analysed “at the beginning of the axitinib treatment”. Of note, all patients must have been previously treated with a TKI. These calculations will be performed on patients who have data on all the variables involved (in the case of a patient who does not have data on all the variables but has > 2 factors, it will be classified in the “Poor” risk group.

Risk groups are defined taking into account the following three factors (Low, Intermediate, High):

- ECOG/PS <1 (related to KPS <80)
- Haemoglobin < LLN
- Corrected calcium >10 mg/dl

The risk groups are as follows:

- Favourable: 0 factors
- Intermediate: 1 factor
- Poor: 2 or 3 factors
- The Objective Response Rate (ORR) is the frequency of subjects with CR or PR.
- The Clinical Benefit Rate is the frequency of subjects with CR, PR or SD.
- Increase of the axitinib dose to above 5 mg twice daily. Defined as having specified "Increase" at least one time, and in this case having specified "New dose" >5 mg/12h.
- Reduction of the axitinib dose to below 5 mg twice daily. Defined as having specified "Reduction" at least one time, and in this case having specified "New dose" <5 mg/12h.

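### The rule for incomplete risk scores (more than 2 factors means Poor) can never apply to the three-factor MSKCC score, and on MSKCC and IMDC it admits incomplete patients only as Poor

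*SAP*

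**What the plan says.** SAP section 7 defines three scores: MSKCC with five factors (before first line), Heng/IMDC with six (at axitinib start and discontinuation), and an MSKCC score for previously treated patients with three (at axitinib start). Under each it says: "These calculations will be performed on patients who have data on all the variables involved". Under each it adds the same exception: "in the case of a patient who does not have data on all the variables but has > 2 factors", the patient goes into the Poor group.

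The cut-offs differ. For MSKCC and IMDC the plan has "Intermediate: 1 or 2 factors", with Poor above 2. For the three-factor score it has "Poor: 2 or 3 factors", with Intermediate at exactly 1.

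Items can be unknown. SAP section 6 records the risk criteria at axitinib start in the form "Corrected calcium >10 mg/dl (Yes/No/Unknown"), and SAP section 8 fills in incomplete dates only. SAP section 7.1 compares the risk groups between long responders and refractory patients at every time point at which they are analysed. The pre-axitinib groups may go on to the logistic model.

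**The concern.** The exception is evidently meant to keep patients whose group is certain although an item is missing. It was written for a Poor cut-off above 2 and repeated under a score whose Poor cut-off is 2. There it has no effect, and patients who are certainly Poor lose their group.

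On the other two scores it works, but for one category only. Whether an incomplete patient is counted then depends on the category itself. The valid-case risk distribution is neither a complete-case distribution nor one of all patients whose group is known. With about 60 patients expected (SAP 2.1), a few patients move the percentages visibly.

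**Working it through.** The plan gives no figure on this point to reproduce.

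**Step 1: logic, no assumptions.** Let k be the known factors present and u ≥ 1 the unknown items. The group is certain if k and k + u fall in the same group. With K items there are 3^K − 2^K incomplete patterns.

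| Score | Incomplete patterns | Admitted by the exception | Certain but dropped |
|---|---|---|---|
| Three-factor | 27 − 8 = 19 | 0 | 3 Poor (k = 2, u = 1) |
| MSKCC | 243 − 32 = 211 | 35, all Poor | 5 × 4 = 20 Intermediate (k = 1, u = 1) |
| IMDC | 729 − 64 = 665 | 191, all Poor | 6 × 5 = 30 Intermediate (k = 1, u = 1) |

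On the three-factor score u ≥ 1 forces k ≤ 2, so more than 2 is impossible. On MSKCC and IMDC every admitted patient is correctly labelled; the issue is who is admitted. No incomplete pattern is certain to be Favourable on any score.

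**Step 2: direction on MSKCC and IMDC.** With n complete cases, a of them Poor, and x admitted patients, the Poor share is (a + x)/(n + x) ≥ a/n. This compares with the complete-case share, under any missingness.

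**Step 3: illustrative size.** The documents give no prevalences or missingness rates. Assumed, with factors independent: poor performance status 15%, haemoglobin 45%, calcium 10%, under one year to treatment 45%, LDH, neutrophils and platelets 15% each; missingness q = 5/10/20% per item or block; 60 patients.

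Three-factor score, items missing independently. The chance of being certainly Poor but dropped is q(1 − q)² × (0.15×0.45 + 0.15×0.10 + 0.45×0.10) = q(1 − q)² × 0.1275. Times 60 this is 0.3/0.6/1.0. With haemoglobin and calcium missing together, only performance status can be the single unknown item: 60 × q(1 − q) × 0.045 = 0.1/0.2/0.4. The Poor share stays at 0.1275 − 2 × 0.00675 = 11.4% throughout, because nobody is admitted.

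MSKCC, items missing independently, q = 10%. Certainly Intermediate but dropped: 60 × 0.1 × 0.9⁴ × 2.242 = 8.8, where 2.242 is the sum over items of the probability that exactly one of the other four factors is present.

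Exact enumeration of all factor and missingness patterns (5/10/20% missing):

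| Score (true Poor) | Missingness | Poor share of valid cases, % | Certainly Intermediate dropped per 60 |
|---|---|---|---|
| MSKCC (9.5%) | all items independent | 10.6/11.9/15.0 | 5.5/8.8/11.0 |
| | time known, calcium and LDH together | 10.0/10.6/11.9 | 2.4/4.4/6.9 |
| | time known, all laboratory items together | 9.8/10.1/10.8 | 1.3/2.4/4.3 |
| IMDC (13.9%) | all items independent | 16.2/18.9/25.9 | 5.9/9.0/9.9 |
| | time known, blood count together | 14.9/16.0/18.6 | 2.2/4.0/6.3 |
| | time known, all laboratory items together | 14.4/14.9/16.0 | 1.2/2.2/4.0 |

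The block rows are the more plausible. The eligibility check in SAP 2.1 includes "Date of first diagnosis, Tumour stage at disease diagnosis, Date of advanced disease diagnosis", SAP section 7 derives "Time (months) between first diagnosis and 1st-line treatment" from dates, and Protocol 8.3 collects "blood count and blood biochemistry", so laboratory values tend to be missing together.

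With equal prevalences of 20-40% and independent missingness, the range widens: MSKCC from 5.8% → 6.5% to 31.7% → 46.0%, IMDC from 9.9% → 11.6% to 45.6% → 67.3%, and 0.3 to 3.7 certainly-Poor patients dropped on the three-factor score.

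**Step 4: can the sign against the true share change?** Yes. If haemoglobin is missing in 30% of patients with the performance-status factor and 10% of others, MSKCC Poor is 9.3% against 9.5%. If every item is missing 30% of the time in Poor patients and 10% in others, MSKCC Poor is 6.3% against 9.5%, and IMDC 10.8% against 13.9%. In that last case complete cases do worse: MSKCC 0.0953×0.7⁵ / (0.0953×0.7⁵ + 0.9047×0.9⁵) = 2.9%, and IMDC, with sixth powers, 3.5%.

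**The case against.** The strongest reply concerns consequence. Each item is also analysed separately (SAP 7.1), and SAP 9.1 prints a percentage with missing values in the denominator beside the valid percentage. Few patients are lost on the three-factor score, and the largest figures for the other two come from the least realistic missingness. This stands and keeps the point minor. The second percentage shows how many patients are unclassified, but not that some of them have a determined group.

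A second reply is that the two halves pull against each other: admitting certainly-Poor patients on the three-factor score would import the same one-sided selection there. This also stands, and is why the wider assignment belongs in a sensitivity analysis. A third is that complete cases are not always nearer the truth, as step 4 shows. That stands too; the gain is a set the reader can identify, with its gaps counted.

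Four stronger readings are tempting, and the documents do not support them:

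- That the exception distorts the three-factor distribution. It is inert there, so the distribution is in effect complete-case.
- That the Poor share on MSKCC and IMDC is always above the true share. Only the comparison with complete cases is certain.
- That the long-responder versus refractory odds ratio is biased. The documents do not say whether missingness differs between response groups.
- That the exception damages the special-interest subpopulation in SAP 7.2. That group excludes Poor patients, and any loss of Favourable or Intermediate patients comes from the complete-data requirement.

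**Conclusion.** The mismatch on the three-factor score and the one-sidedness on MSKCC and IMDC follow from SAP section 7 alone. Their size does not. Under the main assumed prevalences, about 0.1-1.0 certainly-Poor patients per 60 lose their group on the three-factor score at 5-20% missingness. At 10% missingness the Poor share of valid cases is 10.1-11.9% instead of 9.5% on MSKCC and 14.9-18.9% instead of 13.9% on IMDC, the lower ends being for laboratory items missing together.

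These figures assume independent factors and missingness unrelated to risk. The 15% for performance status also assumes that the factor means poor performance status; the pattern logic in step 1 does not depend on how that factor is coded. Severity: minor.

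**What to change.** 1. Report the MSKCC, IMDC and three-factor distributions, and the main table of risk group by response group, on complete cases without the exception. Add an unclassified count by response group.
2. As a sensitivity association analysis, assign every incomplete patient whose known items already fix the group. Three-factor score: at least 2 known factors is Poor. MSKCC and IMDC: more than 2 known factors is Poor, and 1 known factor with exactly 1 unknown item is Intermediate. Take the percentages and the p-value from that same set.
3. Label the change post hoc, since the SAP amendment table shows that version 3 followed a draft of the results.

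Cost: about one SAP sentence per score and a re-run, with no new data. The main table has slightly fewer classified patients. The sensitivity set cannot rescue Favourable patients and must not be read as a distribution: at 20% independent missingness its Favourable share is 12.1% against 19.7% true on MSKCC and 9.3% against 16.7% on IMDC, and its three-factor Poor share is 14.1% against 11.4%.

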## 7.1 PRIMARY OBJECTIVE

In order to meet the study's primary objective, the baseline clinical characteristics of two patient groups with extreme response to the drug will be compared: A group of patients with long-term responses to the drug (long-term responders to axitinib) versus a group of patients with disease progression at the first assessment after the initiation of treatment (group of patients refractory to axitinib).

The classification (in long-term responders or refractory patients) will be based on PFS (in months), as indicated in section 5.2.

It will be shown the following descriptive tables:

- “Long responder” patient (Yes, No). “Long responding patient” is defined if he / she has an PFS  $\geq 9$  months (during axitinib treatment). The 95% CI will be displayed.
- PFS in long responding patients. Only the descriptive analysis of the time in months and the CI for the average, will be shown.
- “Refractory” patient (Yes, No). "Refractory patient" is defined if there is a better response to treatment = PE (to axitinib treatment). 95% CI will be shown.
- PFS in refractory patients. Only the descriptive analysis of the time in months and the CI for the average will be shown.
- Patient group (Long respondent, refractory). It is defined in section 5.2. IC95% will be displayed

At the same time, In addition to comparisons of baseline clinical characteristics between the groups (long-term responders, refractory patients), an association analysis of the following factors with the study groups will be performed:

- Age with respect to first visit ( $\leq 65$  years and  $> 65$  years).
- Age with respect to first diagnosis ( $\leq 65$  years and  $> 65$  years).
- Age with respect to start of axitinib ( $\leq 65$  years and  $> 65$  years).
- Baseline ECOG/PS and at the initiation of first line treatment (0, 1 and  $\geq 2$ ).
- Baseline ECOG/PS and at the initiation axitinib treatment (0, 1 and  $\geq 2$ ).
- Baseline ECOG/PS and at the end of axitinib treatment (0, 1 and  $\geq 2$ ).
- Number of previous treatment lines
- Number of previous treatment lines (1, 2 and  $\geq 3$ )
- Previous nephrectomy (yes and no)
- MSKCC (or IMDC) risk group in all moments in which it is analysed during the study (favourable, intermediate and poor)

- Histology (100% clear cells, primarily clear cells, primarily non-clear cells, 100% non-clear cells)
- Duration of first-line treatment
- Duration of first-line treatment:([0-3] months, [3-6] months, [6-9] months, [9-12] months,  $\geq 12$  months).
- Duration of first-line treatment: ( $\leq 9$ months,  $>9$  months).
- Duration of first-line treatment: ( $\leq 12$ months,  $>12$  months).
- Duration of first-line TKi treatment: ([0-3] months, [3-6] months, [6-9] months, [9-12] months,  $\geq 12$  months).

It will be calculated the duration of the first line, if the drug was only a TKi.

- Duration of first-line TKi treatment: ( $\leq 9$ months,  $>9$  months).
- Duration of first-line TKi treatment: ( $\leq 12$ months,  $>12$  months).
- Duration of the first TKI treatment:( [0-3] months, [3-6] months, [6-9] months, [9-12] months,  $\geq 12$  months).

It will be calculated the duration of the first treatment with a TKi, in 1st or later line (always after axitinib).

- Patients treated with a TKi previous to axitinib other than first. It will be analysed the number of patients with a TKi previous to axitinib, different from the first TKi received.

It will be analysed the duration of this treatment.

- Best response with the TKI received in the first-line (CR, PR, SD, DP)
- Best response with a TKi previous to axitinib with a TKi other than first line (CR, PR, SD, PD).
- Best response with line prior to axitinib with a TKI if a line prior to axitinib other than the first one has been received (CR/PR, SD, DP).
- Number of metastatic locations (1, 2 and  $\geq 3$ ); See this definition in section 7 Definitions of variables and objectives.
- Site of metastases (CNS metastases [yes vs no]; lymph nodes [yes vs no]; lung [yes vs no]; liver [yes vs no]; bone [yes vs no]). In addition to showing the descriptive and comparative table of metastatic locations between groups, another similar table will be shown but with the categories “Hepatic” and “Bone” united in a single.
- Neutrophil/lymphocyte ratio  $\leq 3$  (yes vs no). See this definition in section 7 Definitions of variables and objectives. It will be analysed in all moments included in the study.
- Line of treatment in which it was received.

- 
- Presence of comorbidities.
  - Suspension of treatment.
  - Have you received any further treatment?
  - Has there been disease progression?
  - Best response to treatment (RC, RP, EE, PE).
  - Best response to treatment (RC / RP, EE, PE).
  - Duration of axitinib treatment.
  - Vital status
  - Baseline LDH levels  $>1.5 \times \text{ULN}$  (yes vs no). At the beginning of 1st line
  - Baseline Hgb levels  $\leq \text{LLN}$  (yes vs no). At the beginning of 1st line
  - Baseline corrected Ca++ levels  $>10$  mg/dl (yes vs no). At the beginning of 1st line
  - Baseline neutrophil levels  $> \text{ULN}$  (yes vs no). At the beginning of 1st line
  - Baseline platelet levels  $> \text{ULN}$  (yes vs no). At the beginning of 1st line
  - Smoking habits (smoker, non-smoker or former smoker). At the beginning of 1st line
  - Baseline LDH levels  $>1.5 \times \text{ULN}$  (yes vs no). At the beginning of axitinib treatment
  - Baseline Hgb levels  $\leq \text{LLN}$  (yes vs no). At the beginning of axitinib treatment
  - Baseline corrected Ca++ levels  $>10$  mg/dl (yes vs no). At the beginning of axitinib treatment
  - Baseline neutrophil levels  $> \text{ULN}$  (yes vs no). At the beginning of axitinib treatment
  - Baseline platelet levels  $> \text{ULN}$  (yes vs no). At the beginning of axitinib treatment
  - Smoking habits (smoker, non-smoker or former smoker). At the beginning of axitinib treatment

A logistic regression model will then be carried out to study the association between belonging to each of the two extreme treatment response groups, with each of the possible clinical factors of interest, prior to axitinib treatment. That is, those baseline factors (prior to the start with axitinib) that have been studied in section 7 and that are significant ( $P < 0.05$ ) or close to significance ( $P < 0.15$ ).

The factors in this situation will be summarized below, and that potential prognostic factors of the response to axitinib treatment (long responding group vs refractory group) are considered.

---

The optimal model of prognostic factors will be constructed with the variables that are finally significant ( $P < 0.05$ ).

